**b) CAB LA PrEP: among complete initiators with at least one maintenance injection**

- Total number maintenance injections administered during first period of CAB LA PrEP use (overall and by person)

- Total follow-up time for complete CAB LA initiators with at least one maintenance injection (from first CAB LA PrEP injection to study end, loss to follow-up, death or HIV acquisition, whatever comes first)
- Discontinuation: number of individuals discontinuing CAB LA PrEP and number of individuals resuming LA PrEP injections (additional CAB LA or LEN LA injections after discontinuation and time between the last injection prior discontinuation and the first injection post-discontinuation) or oral PrEP
- Oral bridging between discontinuation of CAB LA injections and resumption of CAB LA injections
- Months on regimen until first censoring (first period of CAB LA PrEP use)  
Calculated as: days from first initiation injection to censoring (study end, loss to follow-up, death, HIV acquisition, discontinuation)
- Cumulative months on regimen across all CAB LA PrEP use (including additional injections after discontinuation)
  - Continuous time on CAB LA PrEP will be calculated as:
    - If no discontinuation: days from first initiation injection to censoring (study end, loss to follow-up, death, HIV acquisition)
    - If discontinuation: days from first initiation injection to discontinuation date (i.e., 127 days after last injection)
  - Among individuals with additional injections after discontinuation, the cumulative months on CAB LA regimen will be calculated across all episodes of continuous CAB LA PrEP use
  - Individuals with incomplete initiation of their first period of CAB LA PrEP use will be excluded from this analysis even if they have additional injections after incomplete initiation
- On CAB LA PrEP at timepoints of interest – among CAB LA users with no discontinuation and among CAB LA users with discontinuation
  - 12 months: injection received between  $\geq 238$  to  $\leq 365$  days after index (up to 127 days before the 12-month mark)
  - 24 months: injection received between  $\geq 603$  to  $\leq 730$  days after index (up to 127 days before the 24-month mark)
  - Study end: injection received up to 127 days before or on study end date
- ◆ **HIV testing & STI testing/screening during first period of PrEP use (Objectives 3.5)**
  - HIV testing
    - Incidence proportion and incidence rate of HIV testing between the start of PrEP and the first discontinuation
    - Timing of HIV tests:
      - Oral PrEP: on-schedule testing defined as receiving an HIV test  $\leq 7$  days before/at start, and 3 months (76-104 days) after each test
      - CAB LA PrEP: on-schedule testing defined as receiving an HIV test

≤7 days before/at first injection, and 14 days prior each subsequent injection

- HIV diagnosis: incidence proportion and incidence rates between index date and the 1st discontinuation
- STI testing/screening
  - Assessed during the first period of PrEP use (oral or injectable)
    - Incidence proportion and incidence rate for STI testing/screening for
      - Gonorrhea
      - Chlamydia
      - Syphilis
      - Chancroid
      - Lymphogranuloma venereum
      - *Mycoplasma genitalium*
      - Hepatitis B virus (HBV)
      - Hepatitis C virus (HCV)
      - Genital Herpes (HSV-1, HSV-2)
      - Trichomoniasis
      - Genital Human papilloma virus (HPV) including warts
    - Interval between the first 2 tests for gonorrhea, chlamydia, syphilis done during the first period of PrEP use
      - Testing 3 months (76-104 days) after last test
      - Testing 6 months (168-196 days) after last test
      - Testing 12 months (351-379 days) after last test
- STI diagnoses
  - New diagnosis of STI as noted in medical record or positive test result
  - STI diagnoses for
    - Syphilis
    - Gonorrhea
    - Chlamydia
    - Chancroid
    - Lymphogranuloma venereum
    - *Mycoplasma genitalium*
    - Hepatitis B virus (HBV)
    - Hepatitis C virus (HCV)
    - Genital Herpes (HSV-1, HSV-2)
    - Trichomoniasis
    - Genital Human papilloma virus (HPV) including warts
- Relevant prescription for a selected list of STIs  
 Proportion of STI diagnosis with a prescription within 14 days following diagnosis as follows:
  - Syphilis: benzathine penicillin G, aqueous crystalline penicillin G, procaine penicillin G + probenecid, doxycycline
  - Gonorrhea: ceftriaxone, ceftriaxone + doxycycline, gentamicin + azithromycin,

- cefixime, cefotaxime
- Chlamydia: doxycycline, azithromycin, levofloxacin, amoxicillin
- Chancroid: azithromycin, ceftriaxone, ciprofloxacin, erythromycin base
- Lymphogranuloma venereum: doxycycline, azithromycin, erythromycin base
- *Mycoplasma genitalium*: doxycycline + azithromycin, doxycycline + moxifloxacin
- Trichomoniasis: metronidazole, tinidazole
- Genital herpes: acyclovir, famciclovir, valacyclovir

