## 5. RATIONALE AND BACKGROUND

HIV remains a persistent problem in the United States (US). In 2023, over 39,000 people were diagnosed with HIV in the US and 6 territories and freely associated states (US CDC, 2025). Over 80% were men, with 66% attributed to male-to-male sexual contact. Hispanic and Black individuals each accounted for more than a third. Ages 15-24 and 25-44 accounted for 18% and 60% of diagnoses, respectively. The South region represented 51% of new cases. The 2021 HIV/AIDS Strategy identified five priority populations disproportionately impacted by HIV: gay, bisexual, and other men who have sex with men (MSM), black women, transgender women, youth aged 13-24 years, people who inject drugs (White House, 2021).

Pre-exposure prophylaxis (PrEP), which consists in the use of antiretroviral medications by HIV-negative individuals with a substantial risk of contracting an HIV infection, is highly effective at preventing HIV when taken as indicated (Cancio-Suárez, 2023). As of August 2025, there are two daily oral medications for PrEP approved by the U.S. Food and Drug Administration (FDA). There are also two FDA-approved long-acting injectable forms of PrEP, one that is administered every other month and the other is administered twice yearly. Oral PrEP was introduced as a form of HIV prevention when the single tablet combination of tenofovir disoproxil fumarate (TDF) and emtricitabine (FTC) was approved by the FDA on July 16, 2012 (Roehr, BMJ 2012). The second oral PrEP option, a single tablet combination of tenofovir alafenamide (TAF) and FTC was approved on October 3, 2019 (The Lancet HIV, 2019).

Cabotegravir long-acting (CAB LA) is an injectable PrEP administered every two months for use in at-risk adults and adolescents and received FDA approval in December 2021 (US FDA, 2021). CAB LA may be initiated with optional short-term oral lead-in (OLI). Clinical trials have demonstrated the superior efficacy of CAB LA PrEP over daily oral TDF/FTC for HIV prevention (Durham, 2023). A second long-acting option for HIV prevention (Lenacapavir - LEN) was approved by the US FDA in June 2025 (Mullard, 2025). It is delivered in subcutaneous injections given every 6 months.

The US Centers for Disease Control and Prevention (CDC) recommend that people consider PrEP if they are HIV negative, have had anal or vaginal sex in the past six months, and have a sexual partner with HIV (especially if the partner has an unknown or detectable viral load), or

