**b) Adherence to CAB LA PrEP schedule**

- Proportion of days covered by CAB LA PrEP in the 12 months following initiation: number of days covered by CAB LA PrEP divided by the number of days in the observation period

Follow-up will be censored at first of:

- a) 12 months after index date
- b) Loss to follow-up
- c) Death
- d) Study end

Coverage by LA PrEP will be determined based on the duration of days covered by the medication, according to the label.

- 1st injection: coverage = 37 days (30 days of coverage + 7-day injection window)
- Subsequent injections: coverage = 67 days (60 days of coverage + 7-day injection window)

Each calendar day will only be counted once, even if there is an overlap between coverage from the prior injection and date of the next injection.

- **Complete versus incomplete initiation:**

- Among all Veterans with  $\geq 1$  CAB LA injection:

→ Complete initiation (2nd injection received within 67 days following the 1st injection)

- 2nd initiation injection on time: 2nd injection between 23 and 37 days following the first injection
- 2nd initiation injection late: 2nd injection between 38 and 67 days following the first injection

→ Incomplete initiation: >67 days without injection following the first injection

- Among incomplete initiators

Any additional injection(s) >67 days after the 1st injection (Yes/no)

If yes:

- o Timing of the 1st additional injection after the last injection of the “incomplete initiation” (interval in days, number with interval of 68-97 days and interval >97 days)
- o Complete versus incomplete reinitiation
- o Interval between the first two reinitiation injections ( $\leq 37$ ; 38-67, 68-97, 98-127;  $\geq 128$  days apart)

• **Timing of CAB LA PrEP maintenance injections:** among complete initiators with at least one maintenance injection

Determined based on the time between initiation injections (Table 3)

- Total number of maintenance injections per individual
- All on time
- Any late maintenance injection (short delays not requiring reinitiation, long delays requiring reinitiation): number of short and long delays, number of individuals with 1, 2, 3 or more short delays, number of individuals with 1, 2, 3 or more long delays, median duration of short and of long delays

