**Table 3:** Timing of CAB LA PrEP maintenance injections, among complete initiators with  $\geq$  maintenance injection

Dosing pattern	Timing of maintenance injections (following previous injection)
On-time	53-67 days
Late	68-127 days
Short delay not requiring reinitiation	68-97 days
Long delay requiring reinitiation	98-127 days
Discontinuation	>127 days without injection

◆ **Patterns of PrEP use (Objective 3.4)**

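### Oral bridging is sought only in gaps of more than 127 days between injections, so oral cover of a typical single missed CAB LA injection is not counted

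*Protocol*

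**What the plan says.** The bridging outcome is worded identically in the Synopsis (Objective 3.4 b), in Section 6 and in Section 7.3.3: "Oral bridging between discontinuation of CAB LA injections and resumption of CAB LA injections". In Section 7.3.3 it applies to Veterans who completed initiation and went on to receive one or more maintenance injections.

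Discontinuation is a defined term. Table 3 gives it as ">127 days without injection". The rule for time on regimen puts a date on it: "days from first initiation injection to discontinuation date (i.e., 127 days after last injection". Table 3 places a gap of 98 to 127 days in a different class, "Long delay requiring reinitiation", and a gap of 68 to 97 days in the short-delay class.

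Section 5 says that CAB LA "is an injectable PrEP administered every two months". Section 7.3.3 sets the coverage of maintenance injections: "Subsequent injections: coverage = 67 days (60 days of coverage + 7-day injection window". The adherence proportion is the "number of days covered by CAB LA PrEP divided by the number of days in the observation period", so oral days are outside its numerator.

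**The concern.** A bridging measure should show whether oral tablets were supplied while injections were interrupted. The plainest case is one missed two-monthly injection covered by tablets, followed by a return at the next due date. Under the protocol's definitions that interval is a long delay and not a discontinuation, so the bridging outcome never examines it.

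Two reported results are affected. The bridging result under Objective 3.4 b) omits this central case. The late-injection results under Objective 3.3 count delays and give their durations, but do not show which of them had oral supply. A reader of the tables could not separate an orally covered absence from a lapse, although Section 7.3.3 already makes oral dispensing a study variable.

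**Working it through.** **Inputs.** Maintenance interval: about 60 days (Section 5, two-monthly; Section 7.3.3, 60 days of coverage). Injection window: 7 days. Coverage of a maintenance injection: 67 days. Coverage of the first injection: 37 days. Discontinuation: a gap over 127 days, dated to day 127 (Table 3 and Section 7.3.3).

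**Step 1: the plan's own use of 127 days.** Section 7.3.3 builds its on-treatment windows from this threshold. 365 - 127 = 238 and 730 - 127 = 603, which match the stated lower bounds at 12 and 24 months. The threshold is thus applied consistently as the definition of discontinuation. It also equals 2 x 60 + 7, which puts one missed injection with a timely return just on the long-delay side.

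**Step 2: the gap left by one missed injection.**

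- Nominal: 2 x 60 = 120 days.
- Return within 7 days of day 120: 113 to 127 days.
- Both intervals free to vary over Table 3's on-time window of 53 to 67 days: 2 x 53 = 106 to 2 x 67 = 134 days.

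**Step 3: classify each gap.** Days beyond injection coverage = gap - 67.

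| Gap (days) | Table 3 class | Days beyond coverage | Eligible as bridging, read literally |
|---|---|---|---|
| 68 | Short delay | 1 | No |
| 97 | Short delay | 30 | No |
| 106 | Long delay | 39 | No |
| 113 | Long delay | 46 | No |
| 120 | Long delay | 53 | No |
| 127 | Long delay | 60 | No |
| 128 | Discontinuation | 61 | Yes |
| 134 | Discontinuation | 67 | Yes |

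The whole 113 to 127 day range is ineligible. On the wider 106 to 134 day range, gaps of 128 to 134 days are eligible.

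**Step 4: the effect of dating discontinuation to day 127.** If bridging must fall after the discontinuation date, the search starts 127 - 67 = 60 days after injection coverage ends. In a 128-day gap, 61 days lie beyond coverage, and 60 of them fall before day 127. If the bullet instead means any oral supply within a gap that ends up over 127 days, this loss disappears. The protocol does not say which is meant.

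**Step 5: one illustrative user.** Injections at days 0, 30, 90, 210, 270 and 330, with the day-150 injection missed. Coverage from the day-90 injection runs to day 156, so days 157 to 209 (53 days) are beyond it. CAB LA days covered over 12 months: (365 - 53)/365 = 312/365 = 85.5%, which is right for that measure. The user has one long delay, no discontinuation and no bridging to count. Assume a full oral supply on days 150 to 209: every day of the year is then covered by one product or the other (365/365), yet these outcomes report the same result as for a user with no tablets.

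**Step 6: does another part of the plan pick this up?** The late-injection outcomes in Section 7.3.3 are counts and durations with no split by oral supply. Resumption with oral PrEP is recorded only after discontinuation. The Objective 3.6 timeline in Section 7.7.1.1 covers only Veterans diagnosed with HIV, and its oral prescriptions are those from before CAB LA began. None of these captures oral supply in a gap of 127 days or less.

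**The case against.** The strongest reply is that the outcome matches its objective. Both are worded in terms of discontinuation and resumption, and no section promises bridging across every delay. The bullet gives no day count or dispensing window, so discontinuation may be meant loosely, and such detail could be settled in the analysis plan, which is not at hand. This stands in part: a loose meaning is possible. But the term is defined in Table 3 and dated in the same subsection, and the protocol states the two ends of the bridging window in three places. A programmer would follow the definition. If any interruption was meant, the wording conflicts with Table 3 and needs correcting anyway.

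Three stronger readings are tempting, and the documents do not support them.

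- A reader might infer that bridging can be found only after two or more missed injections. One missed injection with a return at day 128 or later is a discontinuation and is eligible, and gaps of 128 to 134 days arise even with both intervals inside the on-time window.
- A reader might infer that bridged Veterans are wrongly classed as late, or that their days-covered figure is biased. A 120-day interval is late on the injection schedule whether or not tablets were supplied, and the measure is explicitly of CAB LA days.
- A reader might infer that the comparison of on-time and late users is invalid because late is taken to mean unprotected. The protocol never equates the two; it compares baseline characteristics by injection timing.

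**Conclusion.** The point holds as a matter of outcome definition. Read literally, oral PrEP supplied in any gap of 127 days or less is not counted as bridging. This removes the typical single missed injection (120 days nominally, 113 to 127 days with a return within 7 days of day 120). The day-127 date may also remove up to 60 days of oral cover after the end of injection coverage in Veterans who do discontinue and resume.

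The size of the under-count cannot be estimated. The feasibility count is 748 CAB LA users (Section 7.5), but the documents do not say how many will have gaps of 68 to 127 days or how many of those will have oral supply. The 53-day illustration describes one hypothetical user and is not a bias in the CAB LA measure.

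The conclusion rests on reading discontinuation in the bridging bullet as Table 3 defines it, and on a nominal 60-day interval. It concerns measurement only and says nothing about how a missed injection should be managed. The wording should be settled before the tables are programmed.

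**What to change.** In Section 7.3.3, and in the matching wording of the Synopsis and Section 6, replace the discontinuation-to-resumption window with this rule: assess oral PrEP dispensing in every between-injection gap longer than 67 days, starting from the end of injection coverage. Judge it by the days of supply that fall after day 67, so that tablets dispensed when the injection was due are counted. Report short delays, long delays and discontinuations followed by resumption, each with and without oral supply in the gap. Leave Table 3's thresholds, the late-injection classes and the CAB LA-only days-covered measure unchanged. A days-covered figure for any PrEP, beside the CAB LA figure, is optional.

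The cost is a sentence or two of text and some extra table rows, using oral dispensing data that the study already needs. The downside is small: dispensing is only a proxy for use, as Section 7.9 already acknowledges for oral PrEP, so the new rows show oral supply and not proven protection.

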## **7. RESEARCH METHODS**

### **7.1. Study Design**

This is a cohort study using data from the Veterans Affairs National Sample, which is composed of Veterans who receive healthcare services through the Veterans Health Administration (VHA). This national sample is representative of the Veteran population, capturing a wide range of demographic, clinical, and social characteristics.

Data will be extracted from VHA's Corporate Data Warehouse (CDW), a comprehensive, regularly updated repository of information from VHA's electronic health records and administrative files. It includes patient-level data such as demographics, clinical encounters (diagnoses, interventions), laboratory and imaging results, medication details, health services utilization, and long-term health outcomes.

The study period will range from January 1, 2021, to December 31, 2025. Initiation of PrEP regimen will be assessed during the period January 1, 2021 to June 30, 2025, to allow for at least 6 months of observation following PrEP initiation.

The study will include different cohorts, as described in Table 2.

Veterans who are not on PrEP but could benefit from PrEP will be identified based on risk factors for HIV acquisition or factors linked to behaviors increasing the risk of HIV acquisition which are generally documented in Veterans health records. These risk factors include: tested for or diagnosed with a bacterial STI in the past 12 months (gonorrhea, syphilis, chlamydia) (US CDC, 2024), tested for HIV in the past 12 months, ever had alcohol use disorder (Williams, 2016), ever used illicit non-injection drugs (HIV.gov, 2024), ever used injectable drugs (CDC, 2024), Black women (CDC, 2024; Reaves, 2025), men who have sex with men (CDC, 2022; Mayer, 2021), individuals aged 18-24 years (HIV.gov, 2025 b), any history of PrEP use (Hojilla, 2021; Krakower, 2019).

---

 The US CDC recommends PrEP for people with a bacterial STI diagnosis in the past 6 months. This has been extended to testing for a bacterial STI in the past 12 months for this protocol.

**Table 2:** Description of study cohorts

Objectives	Criteria	
Objective 1a - Among all Veterans without evidence of HIV infection	Population/exposure	No evidence of HIV diagnosis at beginning of each calendar year of the study period under analysis
	Index date	N/A
	Censoring criteria	N/A
	Endpoint	HIV diagnosis

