## 7.2. Study Population and Setting

### 7.2.1. Inclusion criteria

- **Veterans in care without evidence of HIV infection (Obj. 1.1)- individuals will be included if they meet all of the following criteria:**

- At least one VHA health encounter in the calendar year
- $\geq 18$  years of age
- No evidence of HIV infection at the beginning of the calendar year under analysis

- **Veterans in care with a new HIV diagnosis (Obj. 1.2):**

- Incident HIV diagnosis (refer to definition in section 7.3.3)

- **Veterans in care without evidence of HIV infection who are not on PrEP but who could benefit from PrEP (Objective set 2)- individuals meeting all of the following criteria:**

- At least one VHA health encounter during the study period
- $\geq 18$  years of age
- Any of the following criteria indicating that the individual has a risk factor for HIV acquisition or a factor linked to behaviors increasing the risk of HIV acquisition and may benefit from PrEP:
  - tested for or diagnosed with a bacterial STI in the past 12 months (gonorrhea, syphilis, chlamydia),
  - tested for HIV in the past 12 months,
  - ever had alcohol use disorder,
  - ever used illicit non-injection drugs,
  - ever used injectable drugs,
  - Black women,
  - men who have sex with men,
  - individuals aged 18-24 years,
  - any history of PrEP use
- No evidence of HIV infection at the first health encounter with a criteria for PrEP

- **Veterans in care using oral PrEP only (objective set 3)**

- At least one VHA health encounter during the study period
- $\geq 18$  years of age
- Received at least one oral PrEP prescription (TDF/FTC, TAF/FTC) between January 1 2021 and 31 December 2024
- No evidence of HIV infection at the time of the first oral PrEP prescription in the study period
- Have not received a CAB LA PrEP injection between January 1, 2021, and June 30, 2025

- **Veterans in care using CAB LA for PrEP (objective set 3)**

- At least one VHA health encounter during the study period
- $\geq 18$  years of age
- Received at least one CAB LA PrEP injection between January 1, 2021 and June 30, 2025

- No evidence of HIV infection at the time of the first CAB LA PrEP injection in the study period

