**a) Oral PrEP**

- Discontinuation: any discontinuation, resumption of oral PrEP after discontinuation  
Two durations will be used to identify discontinuation of oral PrEP:
  - o Oral PrEP prescription not refilled within 30 days of the previous dispensing
  - o Oral PrEP prescription not refilled within 90 days of the previous dispensing
- Duration of oral PrEP use for the first period of use

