##### **Veterans using PrEP (Objective set 3)**

**Objective 3.1-** Baseline demographic and clinical characteristics will be described at the start of PrEP use during the study period, by regimen type (oral or CAB LA), using median and interquartile ranges for continuous variables and counts and proportions for categorical variables.

**Objective 3.2-** The proportions of Veterans on care initiating CAB LA PrEP who used oral lead in (OLI) and proportion of those with direct to injection (DTI) will be calculated.

**Objective 3.3 and 3.4-** PrEP adherence and usage patterns will be described using median and interquartile range for continuous data as well as absolute and relative frequencies for categorical data. The percentage of days with access to oral PrEP and CAB LA PrEP will be described over the first 12 months after index PrEP initiation. Characteristics of individuals with and without delayed CAB LA injections as well as individuals with and without discontinuation will be compared using Pearson's chi-square tests for categorical variables and Mann-Whitney tests for continuous variables.

**Objective 3.5-** Incidence rates and confidence intervals for HIV testing, HIV diagnosis, STI testing/screening and STI diagnosis will be calculated using univariate Poisson regression. STI treatment prescription will be described using absolute and relative frequencies for categorical data.

**Objective 3.6-** For CAB LA PrEP users diagnosed with HIV, a timeline including details of oral PrEP prescriptions prior to CAB LA PrEP start, injections received, HIV tests performed, HIV treatment, viral load measurements, HIV drug resistance will be provided for each individual.

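### CAB LA months on regimen stop the clock at study end and are summarised by a plain median and IQR, so duration of use is understated by an amount that depends on persistence and start date

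*Protocol*

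**What the plan says.** Duration of use is a named objective for both modalities (protocol section 6, Objectives 3.4a and 3.4b).

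- **CAB LA, first period** (section 7.3.3, among complete initiators with at least one maintenance injection): "Calculated as: days from first initiation injection to censoring (study end, loss to follow-up, death, HIV acquisition, discontinuation"). Discontinuation, the event of interest, is listed together with the reasons for censoring.
- **CAB LA, cumulative months** (same section): users who never stop are counted as "If no discontinuation: days from first initiation injection to censoring (study end, loss to follow-up, death, HIV acquisition"), and users who stop as "If discontinuation: days from first initiation injection to discontinuation date (i.e., 127 days after last injection").
- **Summary** (section 7.7.1.1, Objectives 3.3 and 3.4): "PrEP adherence and usage patterns will be described using median and interquartile range for continuous data". No time-to-event estimator is named anywhere in the protocol.
- **Calendar** (section 7.1): "The study period will range from January 1, 2021, to December 31, 2025", and "Initiation of PrEP regimen will be assessed during the period January 1, 2021 to June 30, 2025".
- **Oral PrEP** (section 7.3.3): "Duration of oral PrEP use for the first period of use" is listed as an outcome, with no rule for users who have not stopped. Section 7.2.1 takes oral-only users with a prescription "between January 1 2021 and 31 December 2024".

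The protocol also plans total follow-up time, the number discontinuing, and the proportion on CAB LA at 12 months, 24 months and study end.

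**The concern.** Study end is the date on which observation stops, not the date on which use stops. For a user still on CAB LA, the elapsed time is only a lower bound on duration. A plain median treats that lower bound as a completed duration.

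The protocol fixes both the variable and its summary, so this is not a detail left open for a later analysis plan. The reported median and quartiles would be too low unless most users stop early. They would also move with the calendar pattern of uptake: two groups with the same persistence but different start dates would show different durations.

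**Working it through.** **No figure to reproduce.** The protocol gives no expected duration or discontinuation rate. Table 4 covers the precision of proportions only. The size therefore has to be shown as a range under assumptions.

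**Inputs from the protocol**
- Last CAB LA start 30 June 2025, data end 31 December 2025: 184 days, or 6.0 months of minimum follow-up.
- FDA approval in December 2021 (section 5): longest follow-up about 48 months.
- Cohort: at least one maintenance injection. Discontinuation is dated 127 days after the last injection; I take that dating as given.
- Earliest on-schedule injections: second at day 23 (section 7.3.3), first maintenance injection 53 days later (Table 3).

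**Step 1. Earliest recordable discontinuation.** 23 + 53 + 127 = day 203, and 203 / 30.44 = 6.67 months. Since 203 exceeds 184, an on-schedule user who starts after about 11 June 2025 cannot be recorded as stopping before study end, yet enters the median with a duration of about 6 months. Any user with an injection after about 26 August 2025 (127 days before study end) is also still on regimen at study end.

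**Step 2. Median that the plan would report.** Assumptions, not from the protocol: no discontinuation before 6.67 months and exponential thereafter with true median m; starts January 2022 to June 2025, either uniform (k = 1) or linearly rising (k = 2); censoring at study end only. The reported median x solves

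exp(−λ(x − 6.67)) × ((48 − x)/42)^k = 0.5, with λ = ln 2 / (m − 6.67).

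For m = 24, λ = 0.6931 / 17.33 = 0.0400:
- k = 1, x = 16.67: exp(−0.0400 × 10.00) = 0.670; 31.33/42 = 0.746; product 0.500.
- k = 2, x = 13.77: exp(−0.0400 × 7.10) = 0.753; (34.23/42)² = 0.664; product 0.500.

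| True median (months) | Reported, uniform | Reported, rising | Relative error | Still on at study end |
|---|---|---|---|---|
| 9 | 8.8 | 8.6 | −3% to −5% | 10–18% |
| 12 | 11.0 | 10.3 | −8% to −14% | 20–33% |
| 24 | 16.7 | 13.8 | −30% to −43% | 50–63% |
| 36 | 19.5 | 15.2 | −46% to −58% | 64–75% |

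The last column is from a simulation of 1,000,000 users per scenario, in which the plain medians agree with the formula and Kaplan-Meier recovers the true median in each row to within 0.1 month.

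**Step 3. Dependence on start date.** In the same simulation with a true median of 24 months for everyone, users with more than 36 months of follow-up show a plain median of 24 months, and those with less than 18 months show 10.5–10.9. The share of variance in recorded duration explained by start date is 0.02–0.05 at a true median of 9 months, 0.08–0.16 at 12, 0.32–0.46 at 24 and 0.47–0.62 at 36.

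**Step 4. Do the planned proportions cover the gap?** A user who starts after 31 December 2024 cannot complete 365 days by study end, and one who starts after 1 January 2024 cannot complete 730. Section 7.3.3 does not restrict the 12- and 24-month denominators to users with enough follow-up, so these figures depend on follow-up too.

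**The case against.** **The label is honest and other measures are planned.** Section 7.3.3 calls the first-period measure months on regimen until first censoring, and reports follow-up time, the number discontinuing and status at fixed times. This stands as mitigation: readers will not see the median alone. It is not a cure, because the named objective is duration of use, the median does not estimate that, and the companion proportions have unrestricted denominators.

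**The bias may be small.** This also stands. Persistence is unknown, and at a true median of 9 months the error is under half a month. The cohort restriction matters as well. An exponential running from the first injection would turn a true 24 months into 12.5–15.3, but it allows discontinuations that on-schedule users with a maintenance injection cannot have. The table in the working respects the restriction.

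**Stronger readings that the protocol does not support**
- A reader might infer that the reported duration mostly reflects start date. No discontinuation rate is given. In the scenarios tabulated, start date explains more than half of the variance only at a true median of 36 months with rising uptake; that reading needs long persistence.
- A reader might extend the error to oral PrEP. The quoted rule is for CAB LA; oral duration has no stated censoring rule. Under the oral window in section 7.2.1, minimum follow-up to study end is 365 days, so administrative censoring leaves a true median of up to about 12 months unchanged. Bias is negligible if first periods, ended by a 30- or 90-day refill gap, are short.
- A reader might see a biased comparison between modalities. No test of duration between oral and CAB LA is planned. Still, section 7.1 gives June 2025 as the end of initiation generally and section 7.2.1 gives December 2024 for oral-only users, so plain medians set side by side would rest on different minimum follow-up.

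**Conclusion.** The point holds for CAB LA months on regimen. As written, ongoing users' truncated time is counted as completed duration, so the median is too low and depends on start date, by an amount set by persistence. Under the stated assumptions the shortfall runs from about 0.2–0.4 months at a true median of 9 months to 7.3–10.2 months at 24 and 16.5–20.8 months at 36. These sizes rest on the assumed exponential shape, the 6.67-month minimum and the uptake pattern; the direction of the error does not.

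This is a should-fix. The outcome is descriptive, and no hypothesis test or decision rule depends on it.

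**What to change.** In sections 7.3.3 and 7.7.1.1 (Objective 3.4):

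1. Estimate time from first injection to first discontinuation by Kaplan-Meier, or by cumulative incidence with death and HIV diagnosis as competing ends of use. Discontinuation is the event; study end and loss to follow-up are censoring. State which handling of death and HIV diagnosis is used.
2. Report the median with a 95% confidence interval, and the curve estimates at 12 and 24 months next to the planned proportions.
3. State that the results are conditional on complete initiation and at least one maintenance injection.
4. Keep the present measure, labelled *observed time on regimen*.
5. Apply the same estimator to first-period oral duration, and write down its censoring rule.

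The cost is a few lines of wording and one standard procedure on variables already derived. The drawback is that the median may not be reached if more than half of users remain on CAB LA; the curve estimates at 12 and 24 months would then carry the result.
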